- j. Subjects discontinuing the study at their request or at the decision of the Investigator prior to Week 56 should be withdrawn from treatment and begin the 24-week Early Termination Follow-Up period described in Section 6.4. Subjects who undergo total joint replacement will be followed for 24 weeks after the procedure as described in Section 6.4.2.
- k. All study activities at dosing visits (Baseline [Day 1] and Weeks 8, 16, 24, 32, 40 and 48), including sample collection, are performed prior to dosing, unless otherwise noted.
- 1. Rescue medication should be discontinued at least 24 hours prior to any on site study visit up to and including Week 64 (including during the Early Termination Follow-Up period). Subjects should return rescue medication bottles at each study visit for assessment of compliance.
- m. If needed, following completion of the visit at which final efficacy assessments are collected (Week 64 and/or 16 weeks after the last dose of investigational product administered), standard of care treatment (as described in Section 5.8.2) may be initiated, and usage recorded on the appropriate concomitant medication CRF.
- n. Samples for Anti-tanezumab Antibody, PK, NGF and biomarkers should be obtained pre-dose (if applicable to the visit). Biomarker samples should be collected at approximately the same time of the day at all scheduled time points and following a fasting period of at least 8 hours.
- o. Serum and urine biomarker sample collections at Weeks 32, 48, 56, 64 and 80 (or at early termination) will occur only for subjects that have activity level monitoring via accelerometry (N ~360).

- p. Subject Daily/Weekly Assessments (IRT) Review of joint pain scores, rescue medication use and concomitant NSAID use entries (refer to Section 7.1). Compliance with IRT assessments is to be reviewed at each study visit, including Phone visits.
- q. Post-baseline MRIs will only be performed for subjects with Kellgren-Lawrence Grade 3 or 4 osteoarthritis in any knee or hip joint, on the basis of the Central Reader's assessment of the Screening X-rays (refer to Section Section 7.3.11).

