## 6.2.6. Week 16 Clinic Visit (Primary Efficacy Time Point)

#### 6.2.6.1. Pre-dosing

• Review subject eligibility.

**NOTE:** At the Week 16 visit, subjects must have a 30% or greater reduction in WOMAC Pain subscale relative to Baseline in the index joint and a 15% or greater reduction in WOMAC Pain subscale from Baseline at either Week 2, 4 or 8 in order to continue investigational product. As a risk mitigation measure, subjects who do not meet this efficacy response criteria will be discontinued from the Double-blind Treatment period and enter the 24-week Early Termination Follow-up period (refer to Section 6.4). The efficacy response calculation will be performed by the IRT system.

- Adverse event review.
- WOMAC (all subscales).
- Patient's Global Assessment of Osteoarthritis.
- WPAI:OA.
- EQ-5D-5L.
- TSQM (v.II).
- mPRTI.
- Lower Extremity Activity Scale (LEAS).
- Vital signs after sitting for at least 5 minutes, (blood pressure, and heart rate).
- Orthostatic blood pressure (supine/standing) measurement.
- Musculoskeletal physical examination.
- Neurologic exam/Neuropathy Impairment Score (referral for neurological consult if required).
- Serum and plasma retention samples.

- Clinical laboratory tests (blood chemistry and hematology).
- Blood sample for PK analysis (refer to Section 7.5).
- Blood sample for anti-tanezumab antibody assessment (refer to Section 7.3.14).
- Blood and urine samples for biomarkers (fasting if possible, urine sample should be from 2nd void of the day or after; refer to Section 7.6).
- Urine pregnancy test for females of childbearing potential (must be negative prior to dosing).
- Sites performing activity level monitoring (actigraphy) will collect activity level monitors from subjects.
- Concomitant medication review/update.
- Subject daily/weekly IRT entry compliance (daily index joint pain score, weekly non-index joint pain assessment and as applicable, daily rescue medication and weekly NSAID use entries).
- Instruct subjects that after the Week 16 visit the index joint pain score, non-index joint pain assessment, rescue medication and NSAID use will all be assessed once weekly using IRT (See Section 7.1).
- Monitor for violations of concomitant NSAID (outside of oral investigational product) use.
- Review daily and weekly (as applicable) joint pain scores.
- Rescue medication (acetaminophen/paracetamol) compliance review/dispense.

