#### Index Joint Pain Assessment

Average pain in the index joint will be assessed by the subject daily from the beginning of the IPAP to the Week 16 Visit, followed by weekly beginning after the Week 16 visit through Week 80 (and weekly during the Early Termination Follow-Up Period).

• Example question when the identified index joint is the right knee:

Select the number that best describes your average pain in your index joint, the right knee in the past 24 hours:

0	1	2	3	4	5	6	7	8	9	10
No Pain										Worst Possible Pain

• Example question when the index joint is the right hip:

Select the number that best describes your average pain in your index joint, the right hip in the past 24 hours:

0	1	2	3	4	5	6	7	8	9	10
No Pain										Worst Possible Pain

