For the analysis of the rescue medication endpoints, missing data is imputed for daily missing scores first, and then the last available weekly score (after daily missing data is imputed) will be used for subsequent missing weekly scores, as described below. For the analysis of the rescue medication endpoints while subjects are still in the study any missing data will be imputed by carrying forward the last recorded daily data up to Week 16 (LOCF daily data). Imputation using the daily data will occur up to the end of the last week when the subject is in the study (see [Appendix 1.1](#) for definitions of the last study day in each week). For example if a subject discontinues on study day 10, then data up to the end of Week 2 will be imputed in this way. The weekly scores for the rescue medication endpoints can then be calculated for each week the subject is in the study. Rescue medication endpoints are summarized and analyzed using LOCF, and so the last weekly score for the rescue medication will be used for LOCF after the subject has discontinued from the study (note, imputation is taken from the last week with non-missing data and not necessarily from the last available study week, eg, if Week 8 is missing then Week 7 data can be used). The baseline observation will not be carried forward in the case where a post-baseline observation is not available for the LOCF imputation. In the example above, the subject who discontinued in Week 2 (Study Day 10) will have their Week 2 value used as the LOCF value for all Weeks 3-16. The BOCF imputation rule will not be used for the subject because rescue medication is collected during the Initial Pain Assessment Period only (days -7 to -1) and subjects should not be taking rescue medication within 24 hours of the Baseline visit (so part of day -1), therefore Baseline rescue medication use is not an accurate reflection of subjects' true Baseline use of rescue medication. Imputation of weekly diary data after Week 56 will not be performed.

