Visit	Target Study Day	Window
Baseline	1 (defined as initial day of study drug administration)	[-7, 1]
Week 8	57	[2, 85]
Week 16	113	[86, 141]
Week 24	169	[142, 225]
Week 40	281	[226, 337]
Week 56	393	[338, 421]
Week 64	449	[422, no upper limit]

WPAI: OA

Visit	Target Study Day	Window
Baseline	1 (defined as initial day of study drug administration)	[-7,1]
Week 16	113	[2,141]
Week 24	169	[142,281]
Week 56	393	[282, 421]
Week 64	449	[422, no upper limit]

Actigraphy, TSQM, mPRTI

Visit	Target Study Day	Window
Baseline	1 (defined as initial day of study drug administration)	[no lower limit, 1]
Week 16	113	[2,253]
Week 56	393	[254, no upper limit]

0900177ed193781b656Approved\Approved On: 08-10-2019 08:56 (GMT)

HCRU

Visit	Target Study Day	Window
Baseline	1 (defined as initial day of study drug administration)	[no lower limit, 1]
Week 64	449	[2,505]
Week 80	561	[506, no upper limit]

For the average pain in the index joint, the data are collected daily via electronic diary up to the end of Week 16, and thereafter weekly up to Week 80. Data up to Week 64 will be reported as part of the efficacy assessment (summary up to Week 64; analysis up to Week 56).

The Baseline score is the mean of the last 3 non-missing pain scores over study days -7 to -1. If fewer than 3 are available between study days -7 and -1, the baseline will be the mean of the available scores.

The table below describes the visit days for each week (Weeks 1-16). All available on-treatment diary data in each of the weekly intervals will be used to calculate the mean daily pain score for that study week.

09001776e1931781b656\Approved\Approved On: 03-10-2019 08:56 (GMT)

Study Week	Days	Study Week	Days
1	1-7	9	57-63
2	8-14	10	64-70
3	15-21	11	71-77
4	22-28	12	78-84
5	29-35	13	85-91
6	36-42	14	92-98
7	43-49	15	99-105
8	50-56	16	106-112

However, if a subject receives the Week 16 injection dose prior to Day 113, the Week 16 score will be calculated using the mean of the available scores from the 7 calendar days immediately prior to the Week 16 injection dose date. Any scores used in this calculation of Week 16 will not also be used in an earlier week calculation, eg, if the Week 16 dose occurs on Day 109, the available scores from Days 102-108 will be used to calculate the average score for Week 16, and the available scores from Days 99-101 will be used to calculate the average score for Week 15.

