During the past 3 months, have you visited the emergency room due to your osteoarthritis?	Yes, No	No = 0 Yes = 1
How many times?	Number of visits	0-999
During the past 3 months, have you been hospitalized due to your osteoarthritis?	Yes, No	No = 0 Yes = 1
How many nights in total did you stay in hospital due to your osteoarthritis in the last 3 months?	Number of Nights	0-999 (max should be 92)
Did you use these aids or devices to help you in doing things because of your osteoarthritis in the last 3 months? 
 • Walking Aid • Wheelchair • Devices or utensils to help you dress, eat or bathe • Other 	Did not use any aids or devices Never, rarely, sometimes, often, always	Did not use any aids or devices = 0 Device not selected = 0 Never = 1 Rarely = 2 Sometimes = 3 Often = 4 Always = 5
Did you quit your job because of your osteoarthritis?	Yes, No	No = 0 Yes = 1 Not applicable = 2
How long ago did you quit your job because of your osteoarthritis?	Years and Months	0-99 Years and 0-99 Months (should be max of 11 months)

090017764931816561Approved\Approved On: 03-10-2019 08:56 (GMT)

Rescue Medication Endpoints

Rescue medication data is collected daily using an electronic system up to Week 16, and weekly after Week 16 and up to Week 80. Daily and weekly collected data will be assigned to a specific study week for summary and reporting. The assignment of daily and weekly data to weeks will use the same principle as described above in [Appendix 1.1](#) for the daily and weekly index joint pain data.

The incidence of rescue medication use will look for any incidence in the week of interest (collected through daily or weekly diary data). The number of days of RM use (using daily and weekly data) and the total amount taken (using daily data up to Week 16 only) over the week will be calculated for the assigned week algorithm described above.

Imputation is described in [Section 7](#) above. Imputation occurs for daily data up to Week 16 where the subject is in the trial and up to the end of that particular week.

An example of imputation and calculating the three endpoints using the daily diary data is shown below.

Example of calculating rescue medication data from Daily Diary Data (Subject does not discontinue)

In this example, a subject has a Week 2 visit on study day 14 (slightly earlier than the nominal day 15). Study days 8-14 would represent Week 2 data.

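### For an early Week 16 visit the diary window moves only if the injection is given, so pain non-responders are measured over a different week from responders

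*SAP*

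**What the plan says.** - **Diary weeks (SAP Appendix 1.1).** Week 15 is Days 99-105 and Week 16 is Days 106-112. There is one exception: "if a subject receives the Week 16 injection dose prior to Day 113, the Week 16 score will be calculated using the mean". That mean is taken over the week that ends the day before the injection. In the SAP's example, "if the Week 16 dose occurs on Day 109, the available scores from Days 102-108 will be used" for Week 16, and Days 99-101 remain as Week 15.
- **Rescue medication (SAP Appendix 2, Rescue Medication Endpoints).** "The assignment of daily and weekly data to weeks will use the same principle as described above in" Appendix 1.1 for index joint pain.
- **Who is injected (Protocol 6.2.6.1 and 6.2.6.2).** WOMAC Pain response is checked before dosing at Week 16, and "subjects who do not meet this efficacy response criteria will be discontinued from the Double-blind Treatment period". Only eligible subjects receive the injection.
- **Visit timing (Protocol Section 6).** The Week 16 visit is Day 113 ± 7 days, that is Days 106-120.
- **End of daily entry (Protocol 7.1.1 and 7.1.2).** Index joint pain is rated daily up to the Week 16 visit, "followed by weekly beginning after the Week 16 visit through Week 80". Rescue use follows the same schedule.
- **Missing days (SAP Section 7).** For rescue use, "any missing data will be imputed by carrying forward the last recorded daily data up to Week 16", and this runs to the end of the last week in which the subject is in the study. Missing daily pain scores stay missing, and the weekly mean uses the days that remain.
- **Abstention (Protocol Table 1, footnote l; also Section 5.9).** "Rescue medication should be discontinued at least 24 hours prior to any on site study visit".
- **On-treatment rule (SAP Section 8).** Diary data count as on-treatment for 84 days after the last SC dose.

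**The concern.** The window moves on receipt of the Week 16 injection. That is a post-randomization event, and a threshold on a co-primary outcome helps decide it. For a responder seen early, Week 16 is the full week before the visit. For a non-responder seen on the same day, Week 16 runs past the visit at which daily entry stops, and the observed days before Day 106 are counted as Week 15.

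The endpoints at stake are Week 16 diary pain and the Week 16 incidence, number of days and amount of rescue use. All are analysed secondary endpoints at the primary efficacy time point. A measurement rule that depends on outcome can distort a comparison between arms whenever the arms differ in the proportion failing the response rule.

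**Working it through.** **1. Reproducing the SAP's examples.** Write *v* for the Week 16 visit day, with the dose given that day.

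- The moved window is Days *v*−7 to *v*−1. For *v* = 109 this is Days 102-108, with Days 99-101 left for Week 15, as in Appendix 1.1.
- The daily carry-forward rule turns 2, –, 0, 1, –, 2, 0 into 2, 2, 0, 1, 1, 2, 0. That is 5 days and 8 × 500 = 4000 mg.
- It turns 1, 1 and five missing days into seven 1s, that is 7 days and 7 × 500 = 3500 mg. Both results match the Rescue Medication Endpoints examples.

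**2. Does another rule remove the later days?** A Week 8 dose within its ±7-day window falls on Days 50-64. Adding 84 gives Days 134-148, so Days 106-112 remain on-treatment. I found no other rule that re-anchors the window for an undosed subject.

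**3. Window days on or after the visit, and rescue score.** Assumptions: the last daily entry is on day *v*−1 and no later entry falls in the window. For an undosed subject, the number of days in 106-112 on or after the visit is 113 − *v*.

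Take a subject who uses rescue every day but abstains on day *v*−1. Undosed, only Days 106 to *v*−2 show use and the zero on day *v*−1 is carried forward, so the score is max(0, *v* − 107). Dosed, the score is 7 − 1 = 6.

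| Visit day *v* | Window days on or after visit | Rescue days, undosed | Rescue days, dosed |
|---|---|---|---|
| 106 | 7 | 0 | 6 |
| 107 | 6 | 0 | 6 |
| 108 | 5 | 1 | 6 |
| 109 | 4 | 2 | 6 |
| 110 | 3 | 3 | 6 |
| 111 | 2 | 4 | 6 |
| 112 | 1 | 5 | 6 |

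Most of the window lies on or after the visit only for *v* = 106-109.

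**4. Sensitivity to the last record.** Suppose instead random use on 3/7 of days (an illustrative value).

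- With abstention on day *v*−1, the mean is max(0, *v* − 107) × 3/7 undosed, against 6 × 3/7 = 2.57 dosed. This gives 0.00 at *v* = 106, 0.86 at *v* = 109 and 2.14 at *v* = 112.
- Without abstention, the carried value is as likely as any other day to show use, and the means agree at 7 × 3/7 = 3.00.
- A daily user who does not abstain scores 7 in both groups.

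The low score therefore comes from carrying forward the abstention day, not from missing days as such.

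**5. Diary pain.** With *v* = 106 and no later entry, the undosed subject has no score in Days 106-112. SAP Section 7 then treats this as a discontinuation on the pain criteria and imputes around baseline, although Days 99-105 were observed.

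**6. After the change.** If the window is Days *v*−7 to *v*−1 for every early visit, the abstaining daily user scores 6 in both groups for each *v* from 106 to 112.

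**The case against.** The rule has a sensible purpose: it keeps days after a new injection out of Week 16. Undosed subjects have no such days, and with a Week 8 dose on Day 57, Days 106-112 still lie inside the 8-week dosing interval (57 + 56 = 113). This explains the choice of trigger. It does not explain why days after daily entry has ended should stand for Week 16 when a full observed week is available.

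Several stronger readings are tempting, and the documents do not support them.

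- **Rescue use is always understated in non-responders.** Missing days are carried forward, not set to zero, and the SAP's own discontinuation example scores 7 of 7 days. Even a compliant subject need not record a zero: entries use a 24-hour recall, so an evening entry on the day before the visit can cover hours before abstention began. After withdrawal, Protocol 5.9 does not repeat the limit of 3 days per week, so any later entries in the window could raise the score. SAP Appendix 1.1 also allows that the weekly diary may not be activated at the visit.
- **The treatment ratio is biased toward 1.** This needs more non-responders in the NSAID arm and mostly zero last records. Both are assumptions.
- **A sizeable share of each arm is affected.** Visits spread evenly over Days 106-120 would put 7/15 = 47% before Day 113, but Protocol Section 6 asks for scheduling by the baseline date as far as possible. Neither document gives a failure rate for the response rule.
- **The distorted score runs on to Week 56.** Weekly entries continue in follow-up and count as on-treatment up to 84 days after the last dose, so they may replace it.

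It is also fair to say that the consequence is limited. The co-primary WOMAC and Patient's Global Assessment endpoints use the visit window of Days 86-141, the key secondary endpoint is WOMAC-based, and the diary endpoints carry no multiplicity control.

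**Conclusion.** The point holds as a small defect. For visits on Days 106-112, the week measured by the diary depends on whether the subject passed the WOMAC Pain response rule, and nothing else in the SAP corrects this.

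For an undosed subject, between 7 days (visit on Day 106) and 1 day (visit on Day 112) of the window falls on or after the visit. Week 16 rescue use is understated where the last daily record is zero: by 6, 6, 5, 4, 3, 2 and 1 days for an abstaining daily user seen on Days 106 to 112, assuming that daily entry ends the day before the visit and no later entry falls in the window. It is not understated where that record shows use, and entries made after withdrawal could also remove the shortfall. Diary pain can be wholly missing at Week 16 for a Day 106 visit.

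The number of subjects affected, and the size and direction of any effect on the treatment contrasts, cannot be derived from the documents. The co-primary and key secondary results are not touched.

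**What to change.** In SAP Appendix 1.1, make the trigger a Week 16 visit before Day 113 instead of receipt of the Week 16 injection before Day 113, and count the 7 calendar days back from the visit date instead of the injection date. State in the Rescue Medication Endpoints text that the same anchor applies there. Every subject with an early visit then uses the 7 days before it, and subjects dosed at that visit keep their present window. The cost is one sentence in the SAP and one anchor date in the derivation program.

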Appendix 1.2. Definition of Protocol Deviations that Relate to Statistical Analyses/Populations

Not applicable.

Appendix 1.3. Definition of Analysis Populations/Sets

Not applicable.

Appendix 1.4. Further Definition of Endpoints

Health State Utility of the EQ-5D-5L

The EQ-5D-5L contains five questions that measure the following dimensions: mobility, self-care, usual activities, pain/discomfort, and anxiety/depression. Each of the five dimensions has five levels: (1) no problems; (2), slight problems; (3) moderate problems; (4) severe problems; and (5) extreme problems.

The health utility scores are defined for every possible set of outcome combinations of the five dimensions for the following countries:

- Denmark, France, Germany, Japan, the Netherlands, Spain, Thailand, UK, US and Zimbabwe

This study recruited treated subjects from the following countries.

- Australia, Bulgaria, Brazil, Colombia, Japan, New Zealand, Peru, Philippines, Russia, South Korea, Taiwan, Ukraine, US, Croatia, Lithuania, Serbia and Slovakia

Some of these may not actually recruit or treat subjects, and other countries may be added. As there is a mismatch between countries where subjects are being recruited and the currently available EQ-5D-5L health utility scoring, we will assign subjects to the following scoring countries based on the following assignments.

EQ-5D-5L Scoring Country	Study Recruitment Country
Denmark	-
France	-
Germany	Russia, Ukraine, Croatia, Lithuania, Serbia, Slovakia, Bulgaria
Japan	Japan, South Korea, Taiwan
The Netherlands	-
Spain	Colombia, Peru
Thailand	-
UK	Australia, New Zealand
US	Brazil, US, Philippines

0900177641937816160ApprovedApproved On: 03-Oct-2019 08:56 (GMT)

Zimbabwe	-
----------	---

If more EQ-5D-5L utility scores become available or other countries are added, then this assignment may be modified.

The health utility for a subject with no problems in all 5 items is 1 for all countries (except for Zimbabwe where it is 0.9), and is reduced where a subject reports greater levels of problems across the five dimensions. The minimum score across the countries is -0.654.

09001776e193181b6156\Approved\Approved On: 08-10-2019 08:56 (GMT)

Appendix 2. WPAI:OA Endpoints

The tables below summarizes the 6 questions of the WPAI:OA questionnaire, and the four endpoints of the effect of impairment on activity and impairment.

Question	Question Wording	Scoring
1	Are you currently employed? [if No skip to question 6]	Yes, No
2	During the past seven days, how many hours did you miss from work due to problems associated with your OA of the knee or hip	number of hours (free text)
3	During the past seven days, how many hours did you miss from work because of any other reason, such as vacation, holidays, time off to participate in this study?	number of hours (free text)
4	During the past seven days, how many hours did you actually work (if '0' skip to Question 6)	number of hours (free text)
5	During the past seven days, how much did your OA of the knee or hip affect productivity while you were working?	0 to 10 scale with 0 being 'No effect on my work' and 10 being 'Completely prevented me from working'
6	During the past seven days, how much did your OA of the knee or hip affect your ability to do your regular daily activities, other than work at a job?	0 to 10 scale with 0 being 'No effect on my daily activities' and 10 being 'Completely prevented me from doing my daily activities'

WPAI endpoint	Calculation
Percent activity impairment due to Osteoarthritis	$Q6 * 10$
Percent impairment while working due to osteoarthritis	$Q5 * 10$
Percent overall work impairment due to osteoarthritis	$\left\{ \frac{Q2}{Q2 + Q4} + \left[1 - \left(\frac{Q2}{Q2 + Q4} \right) \right] \left(\frac{Q5}{10} \right) \right\} * 100$
Percent work time missed due to Osteoarthritis	$\frac{Q2}{Q2 + Q4} * 100$

0900177 (e-s) 1810156 Approved Approved On: 08-10-2019 08:56 (GMT)

TSQM vII

The 11 questions of the TSQM and the scoring are shown below:

Item	Question wording	Likert Scoring
1	How satisfied or dissatisfied are you with the ability of the medication to prevent or treat the condition?	1 (Extremely dissatisfied) to 7 (Extremely satisfied)
2	How satisfied or dissatisfied are you with the way the medication relieves symptoms?	1 (Extremely dissatisfied) to 7 (Extremely satisfied)
3	As a result of taking this medication, do you experience any side effects at all?	0 (No), 1 (Yes)
4	How dissatisfied are you by side effects that interfere with your physical health and ability to function (eg, strength, energy levels)?	1 (Extremely dissatisfied) to 5 (Not at all dissatisfied)
5	How dissatisfied are you by side effects that interfere with your mental function (eg, ability to think clearly, stay awake)?	1 (Extremely dissatisfied) to 5 (Not at all dissatisfied)
6	How dissatisfied are you by side effects that interfere with your mood or emotions and ability to function (eg, anxiety/fear, sadness, irritation/anger)?	1 (Extremely dissatisfied) to 5 (Not at all dissatisfied)
7	How satisfied or dissatisfied are you with how easy the medication is to use?	1 (Extremely dissatisfied) to 7 (Extremely satisfied)
8	How satisfied or dissatisfied are you with how easy it is to plan when you will use the medication each time?	1 (Extremely dissatisfied) to 7 (Extremely satisfied)
9	How satisfied or dissatisfied are you by how often you are expected to use/take the medication?	1 (Extremely dissatisfied) to 7 (Extremely satisfied)
10	How satisfied are you that the good things about this medication outweigh the bad things?	1 (Extremely dissatisfied) to 7 (Extremely satisfied)
11	Taking all things into account, how satisfied or dissatisfied are you with this medication?	1 (Extremely dissatisfied) to 7 (Extremely satisfied)

The scoring of the 4 satisfaction parameters are shown in the table below.

TSQM Parameter	Scoring
Effectiveness	$[(\text{Item 1} + \text{Item 2}) - 2] / 12 * 100$
Side Effects	$[(\text{Item 4} + \text{Item 5} + \text{Item 6}) - 3] / 12 * 100$ If one item is missing then: $[(\text{Sum of two completed items}) - 2] / 8 * 100$
Convenience	$[(\text{Item 7} + \text{Item 8} + \text{Item 9}) - 3] / 18 * 100$ If one item is missing then: $[(\text{Sum of two completed items}) - 2] / 12 * 100$
Global Satisfaction	$[(\text{Item 10} + \text{Item 11}) - 2] / 12 * 100$

The four parameters have a scale of 0-100, with 100 being the best (most satisfied) score.

0900177 (e-s) 1811656 Approved Approved On: 03-10-2019 08:56 (GMT)

Healthcare Resource Utilization (example using 3 month recall—8 week recall is also used in study)

Question	Response	Scoring
During the last 3 months, what services did you receive directly related to your osteoarthritis? 
 • Primary Care Physician • Neurologist • Rheumatologist • Physician Assistant or Nurse Practitioner • Pain Specialist • Orthopedist • Physical Therapist • Chiropractor • Alternative Medicine or Therapy • Podiatrist • Nutritionist/Dietician • Radiologist • Home healthcare services • Other 	Number of Visits	Response not selected = 0 Number of visits = 1-999
During the past 3 months, have you visited the emergency room due to your osteoarthritis?	Yes, No	No = 0 Yes = 1
How many times?	Number of visits	0-999
During the past 3 months, have you been hospitalized due to your osteoarthritis?	Yes, No	No = 0 Yes = 1
How many nights in total did you stay in hospital due to your osteoarthritis in the last 3 months?	Number of Nights	0-999 (max should be 92)
Did you use these aids or devices to help you in doing things because of your osteoarthritis in the last 3 months? 
 • Walking Aid • Wheelchair • Devices or utensils to help you dress, eat or bathe • Other 	Did not use any aids or devices Never, rarely, sometimes, often, always	Did not use any aids or devices = 0 Device not selected = 0 Never = 1 Rarely = 2 Sometimes = 3 Often = 4 Always = 5
Did you quit your job because of your osteoarthritis?	Yes, No	No = 0 Yes = 1 Not applicable = 2
How long ago did you quit your job because of your osteoarthritis?	Years and Months	0-99 Years and 0-99 Months (should be max of 11 months)

090017764931816561Approved\Approved On: 03-10-2019 08:56 (GMT)

Rescue Medication Endpoints

Rescue medication data is collected daily using an electronic system up to Week 16, and weekly after Week 16 and up to Week 80. Daily and weekly collected data will be assigned to a specific study week for summary and reporting. The assignment of daily and weekly data to weeks will use the same principle as described above in [Appendix 1.1](#) for the daily and weekly index joint pain data.

The incidence of rescue medication use will look for any incidence in the week of interest (collected through daily or weekly diary data). The number of days of RM use (using daily and weekly data) and the total amount taken (using daily data up to Week 16 only) over the week will be calculated for the assigned week algorithm described above.

Imputation is described in [Section 7](#) above. Imputation occurs for daily data up to Week 16 where the subject is in the trial and up to the end of that particular week.

An example of imputation and calculating the three endpoints using the daily diary data is shown below.

Example of calculating rescue medication data from Daily Diary Data (Subject does not discontinue)

In this example, a subject has a Week 2 visit on study day 14 (slightly earlier than the nominal day 15). Study days 8-14 would represent Week 2 data.

Using the Week 2 interval described above for a subject, ie, study days [8-14], we have the following rescue medication example data.

The amount taken and number of days of rescue medication use is adjusted for the duration of the Weekly interval.

09001776e1931781b6561ApprovedApproved On: 03-10-2019 08:56 (GMT)

Study Day (Week)	Number of Doses of RM taken [1]	Number of Doses of RM taken [1] with LOCF imputation
8 (Week 2)	2	2
9 (Week 2)	Missing	2 [2]
10 (Week 2)	0	0
11 (Week 2)	1	1
12 (Week 2)	Missing	1 [2]
13 (Week 2)	2	2
14 (Week 2)	0	0

[1] 500mg tablets of acetaminophen; [2] Using LOCF imputation for missing data

For this subject the following data will be calculated for Week 2:

- Incidence of rescue medication taken in Week 2: Yes. Rescue medication taken on days 8, 9 (imputed), 11, 12 (imputed), 13.
- Number of days of rescue medication use in Week 2: 5. For days 8-14 we have rescue medication taken on days 8, 9 (imputed), 11, 12 (imputed), and 13. The number of days taken for the 7 day period is $5/7*7=5$.
- Amount (mg) of rescue medication use in Week 2: For days 8-14 we have the number of doses taken of 2, 2 (imputed), 0, 1, 1 (imputed), 2, and 0. The number of doses taken for the 7 day period is $8/7*7=8$, making the amount of acetaminophen dosage of 4000mg.

Example of calculating rescue medication data from Daily Diary Data (Subject discontinues)

In this example, a subject discontinues on study day 62, a few days after a Week 8 visit (which was on study day 60). The Week 5-8 data is calculated as described above (eg, Week 8 using days [50, 56]). The subject has rescue medication data as shown below.

09001776e1931781b6561Approved\Approved On: 08-10-2019 08:56 (GMT)

Study Day (Week)	Number of Doses of RM taken [1]	Number of Doses of RM taken [1] with LOCF imputation
57 (Week 9)	1	1
58 (Week 9)	1	1
59 (Week 9)	Missing	1 [2]
60 (Week 9)	Missing	1 [2]
61 (Week 9)	Missing	1 [2]
62 (Week 9)	Missing	1 [2]
63 (Week 9)	Missing	1 [2]

[1] 500mg tablets of acetaminophen; [2] Using LOCF imputation for missing data

Week 9 is calculated as days 57 to 63. The data up to the end of the last week the subject was in the trial is imputed using LOCF as shown above. Therefore the Week 9 scores are then used to impute the Weekly data for summary and analysis for Weeks 10 to 56 (up to Week 16 for the amount of rescue medication use).

As above the incidence of rescue medication for Week 9 would be ‘Yes’. The number of days of rescue medication use would be 7, and the average dose would be $7/7*7*500=3500\text{mg}$ for this week.

09001776e1931781b656\Approved\Approved On: 08-10-2019 08:56 (GMT)

